8.3.2 Tissue Biomarkers

PD-L1 testing will be performed by the CRO QualTek Molecular Laboratories. Any archived tissue samples or tissue obtained from brain biopsy prior to enrollment (archival tissue) and those obtained at suspected radiographic progression will be sent to the CRO for PD-L1 expression assay. We will correlate outcomes and imaging findings with PD-L1 expression in archival systemic tumor tissue, brain biopsy prior to enrollment, and tissue obtained at

persistent radiographic progression. Frozen tissue and fixed tissue blocks from initial lung biopsies will be used. In a subset frozen sections and fixed tissue blocks from subjects who undergo resection of brain metastases for clinical indications will also be utilized.

9.0 ADVERSE EVENTS

9.1 Adverse Event (AE) Monitoring

The investigator or qualified designee will assess each subject to evaluate for potential new or worsening AEs as specified in the Schedule of Events and more frequently if clinically indicated. All adverse events will be monitored continuously by the PI in order to stop treatment as soon as a subject experiences grade 3 or greater AE attributed to pembrolizumab, ferumoxytol, or both. Adverse experiences will be graded and recorded throughout the study and during the follow-up period according to NCI CTCAE Version 4.0. Toxicities will be attributed and graded, and action taken with regard to trial treatment will be recorded.

AEs will be attributed as unrelated, related or possibly related to:

- 1) pembrolizumab
- 2) ferumoxytol
- 3) standard of care therapies:
 - Arm 1: stereotactic radiosurgery
 - Arm 2: radiation and temozolomide

For subjects receiving treatment with pembrolizumab, all AEs of unknown etiology associated with Pembrolizumab exposure should be evaluated to determine if it is possibly an event of clinical interest (ECI) of a potentially immunologic etiology (termed immune-related adverse events, or irAEs).

9.2 Sponsor Responsibility for Reporting Adverse Events

All Adverse Events will be reported to regulatory authorities, IRB/IECs and investigators in accordance with all applicable global laws and regulations.

9.3 OHSU IRB Reporting of Reportable New Information and Adverse Events (only if applicable)

Reportable New Information (RNI) and Adverse Events (AE) will be reported to IRB according to the policies, procedures and guidelines posted on the OHSU IRB web site:

- Fatal and life-threatening RNI will be reported to OHSU IRB within 5 days of notification of the event. All other reports will also be submitted to OHSU IRB no later than 5 days of occurrence or notification of the event. Copies of the report documents will be kept in the study regulatory binder.
- Reportable New Information is submitted through OHSU eIRB and will be reviewed by OHSU Knight Cancer Institute and IRB.

9.4 Assessing and Recording Adverse Events

An adverse event is defined as any untoward medical occurrence in a patient or clinical investigation subject administered a pharmaceutical product and which does not necessarily have to have a causal relationship with this treatment. An adverse event can therefore be any

unfavorable and unintended sign (including an abnormal laboratory finding, for example), symptom, or disease temporally associated with the use of a medicinal product or protocol-specified procedure, whether or not considered related to the medicinal product or protocol-specified procedure. Any worsening (i.e., any clinically significant adverse change in frequency and/or intensity) of a preexisting condition that is temporally associated with the use of the Merck's product, is also an adverse event.

Changes resulting from normal growth and development that do not vary significantly in frequency or severity from expected levels are not to be considered adverse events. Examples of this may include, but are not limited to, teething, typical crying in infants and children and onset of menses or menopause occurring at a physiologically appropriate time. Merck product includes any pharmaceutical product, biological product, device, diagnostic agent or protocol-specified procedure, whether investigational (including placebo or active comparator medication) or marketed, manufactured by, licensed by, provided by or distributed by Merck for human use.

Adverse events may occur during the course of the use of Merck product in clinical trials or within the follow-up period specified by the protocol, or prescribed in clinical practice, from overdose (whether accidental or intentional), from abuse and from withdrawal. Adverse events may also occur in screened subjects during any pre-allocation baseline period as a result of a protocol-specified intervention, including washout or discontinuation of usual therapy, diet, placebo treatment or a procedure.

Progression of the cancer under study is not considered an adverse event unless it is considered to be drug related by the investigator.

All adverse events will be recorded from the time the consent form is signed through 30 days following cessation of treatment and at each examination on the Adverse Event case report forms/worksheets.

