3.0 OBJECTIVES

3.1 Primary Objective

Determine the sensitivity and specificity of relative cerebral blood volume (rCBV) measured by steady state MRI with ferumoxytol in identifying true vs pseudoprogression in patients with newly diagnosed GBM receiving pembrolizumab with standard of care chemo-radiation.

3.2 Secondary Objectives:

1. Determine the safety and toxicity of pembrolizumab when used in combination with standard of care chemo radiation.
2. Determine the progression free survival (PFS), overall survival (OS), clinical response and duration of best response.

Rationale: Given the relatively small sample size, we aim to collect preliminary data on safety and toxicity as well as progression free survival, overall survival, best response and duration of best response survival. Data from this pilot study will be used to power a larger study.

3.3 Exploratory Objectives:

1. Compare the immune response as determined by the volume, pattern and intensity of delayed (24hr) ferumoxytol uptake between subjects who develop true vs pseudoprogression. This is optional and will be performed only in patients who have provided additional consent.
2. Investigate the serum immunological parameters (serum biomarker) and correlate clinical as well as radiological response with systemic immune response to pembrolizumab as measured by immunological panel.

3. Compare the changes in PDL-1 expression in the biopsy tissue before and after therapy at the time of progression and correlate PD-L1 expression with response rates and survival.
4. In subjects in metastatic arm with any measurable systemic lesions, investigate the feasibility of measuring vascular volume fraction (VVF), vessel size index (VSI) and vessel density index (VDI) as surrogate for response (true vs pseudoprogression, as determined by RECIST 1.1 and irRC [1, 2].

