A major challenge in managing and designing trials for brain tumors is determining tumor response to therapy, and then differentiating response from recurrence or treatment-related changes. After radiation, a large majority of these tumors can paradoxically increase in size due to an inflammatory response called ‘pseudoprogression’. The term pseudoprogression describes the phenomenon of subacute radio-chemotherapy treatment-related sequelae in patients with brain tumors that presents as increasing or new contrast enhancement on MRI [46, 47]. These patients stabilize or recover spontaneously, usually without any change in treatment. As cancer immunotherapeutics are being tested in clinical trials, pseudoprogression is increasingly becoming a growing challenge that needs to be addressed [48]. It is estimated that over 10 -12% of patients develop pseudoprogression before eventually showing a response that can be captured by conventional response assessment criteria after immunotherapy. Similarly, over 30% develop imaging changes that are consistent with pseudoprogression after radiation [49]. This number is significantly higher when immunotherapy is combined with standard of care radiation. Current standard of care imaging or response assessment criteria do not have the ability to differentiate this immune response from true progression at any given time point.

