- **Confirmation of true progression:** For the purpose of this study, Histopathologic evidence of viable tumor cells in patients with persistent radiographic progression will be define to have confirmed true progression. True progression is confirmed by histopathology, Pembrolizumab will be stopped and patient swill be taken off-study.. Patients who refuse biopsy or biopsy is not deemed clinically necessary will be taken off study at persistent radiographic progression. However, they will be continued to be monitored with clinical MRI scan and until death.
- **Pseudoprogression (PsP):** for the purpose of this pilot study, PsP may be confirmed by imaging or by pathology.
 - PsP Imaging: stable or decrease in volume of enhancement at 4 weeks (\pm 5 days) after suspected radiographic progression.
 - PsP pathology: No viable tumor tissue is seen by histopathology evaluation on tissue obtained after confirmed radiographic progression by imaging.
- **Clinical progression:** Subjects may be removed from study if they experience symptomatic deterioration without radiographic evidence of disease progression.

Not evaluable (NE): Only relevant if any of the target lesions had additional interventions for clinical managements, patient is unable to get follow up scans or images are of poor quality.

Duration of Best Response: The duration of best response is measured from the time measurement criteria are met for SD, CR or PR (whichever is first recorded) until the first date that recurrent or PD is objectively documented (taking as reference for PD the smallest measurements recorded since the treatment started).

Progression free survival and overall survival will be calculated from the date of diagnosis to the date of confirmed progression or death, respectively. The date of diagnosis was used because the time between the date of diagnosis and the start of treatment or date of enrollment may vary due to subject variables or logistical issues based on radiation planning.

Systemic Lesions (only for Arm 1):

Measurements based on RECIST version 1.1 will be used to make a diagnosis of suspected systemic progression; it will be confirmed using irRC at follow-up.

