9.6.4 Immediate Reporting of Adverse Events to the Sponsor and to Merck

9.6.4.1 Serious Adverse Events

A serious adverse event is any adverse event occurring at any dose or during any use of Merck’s product that:

- Results in death;
- Is life threatening;
- Results in persistent or significant disability/incapacity;
- Results in or prolongs an existing inpatient hospitalization;
- Is a congenital anomaly/birth defect;

- Is a new cancer (that is not a condition of the study);
- Is associated with an overdose;
- Is another important medical event

Refer to Table 8 for additional details regarding each of the above criteria.

Any serious adverse event, or follow up to a serious adverse event, including death due to any cause other than progression of the cancer under study that occurs to any subject from the time the consent is signed through 90 days following cessation of treatment, or the initiation of new anti-cancer therapy, whichever is earlier, whether or not related to Merck product, must be reported within 24 hours to the Sponsor and within 2 working days to Merck Global Safety.

Non-serious Events of Clinical Interest will be forwarded to Merck Global Safety and will be handled in the same manner as SAEs.

Additionally, any serious adverse event, considered by an investigator who is a qualified physician to be related to Merck product that is brought to the attention of the investigator at any time outside of the time period specified in the previous paragraph also must be reported immediately to the Sponsor and to Merck.

SAE reports and any other relevant safety information are to be forwarded to the Merck Global Safety [contact]

A copy of all 15 Day Reports and Annual Progress Reports is submitted as required by FDA, European Union (EU), Pharmaceutical and Medical Devices agency (PMDA) or other local regulators. Investigators will cross reference this submission according to local regulations to the Merck Investigational Compound Number (IND, CSA, etc.) at the time of submission. Additionally investigators will submit a copy of these reports to Merck & Co., Inc. (Attn: Worldwide Product Safety; [contact]) at the time of submission to FDA.

All subjects with serious adverse events must be followed up for outcome.

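### Progression is exempt from AE and SAE reporting with no standard of proof, so inflammatory events labelled as progression can be missing from the safety estimate

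*Combined protocol and SAP*

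**What the plan says.** Two safety sections carve out progression. Section 9.4: "Progression of the cancer under study is not considered an adverse event unless it is considered to be drug related by the investigator". Section 9.6.4.1, listing what must be reported within 24 hours to the sponsor, covers serious events "including death due to any cause other than progression of the cancer under study". Neither section defines progression, sets a level of evidence for it, or refers to Section 8.1.

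Section 8.1 does have a tissue standard: "Histopathologic evidence of viable tumor cells in patients with persistent radiographic progression will be define to have confirmed true progression". It also lets subjects leave the study without meeting it. On biopsy: "Patients who refuse biopsy or biopsy is not deemed clinically necessary will be taken off study at persistent radiographic progression". Under the heading of clinical progression: "Subjects may be removed from study if they experience symptomatic deterioration without radiographic evidence of disease progression".

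Section 4.0, on pseudoprogression, explains why tissue matters: "Current standard of care imaging or response assessment criteria do not have the ability to differentiate this immune response from true progression", a limitation stated for any single time point.

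Secondary objective 1 (Section 3.2) is: "Determine the safety and toxicity of pembrolizumab when used in combination with standard of care chemo radiation". Section 10.0 analyses adverse event rates as proportions with exact 95% confidence intervals.

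**The concern.** Exempting progression from AE reporting is ordinary in oncology, where progression can usually be recognised. This protocol starts from the premise that it often cannot be: an inflammatory reaction to radiation plus PD-1 blockade can look like tumour growth on standard imaging. The plan asks for tissue before it calls progression true for the imaging endpoint, but asks for no particular evidence before an event leaves the safety data on the same ground.

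The error runs in one direction. An inflammatory event labelled progression is not counted as toxicity, so the safety estimate can only be lowered. Serious neurological toxicity is the kind of event most likely to be confused with progression here, and Section 3.2 says that data from this pilot will be used to power a larger study.

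**Working it through.** **1. Routes to a progression label without tissue**

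- Persistent radiographic progression with biopsy refused or not judged necessary (Section 8.1).
- Symptomatic decline with no imaging evidence, called clinical progression (Section 8.1). Table 6 in Section 7.12 names encephalitis as an immune-related event.
- Death in the four weeks between suspected progression and the confirmatory scan. Tissue is sought only after persistence is shown.

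**2. Whether other provisions catch such an event**

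- The drug-related exception in Section 9.4 asks the investigator to make the distinction that Section 4.0 calls unreliable on standard imaging. It says drug related, whereas Section 9.1 also allows a possible relationship and Section 5.4.1 counts one.
- Section 9.1 sends AEs of unknown cause for evaluation as events of clinical interest, but only once they are classed as AEs. The exemption acts before that step. The list in Section 9.6.4.2 holds overdose and a liver criterion, and no CNS event.
- Section 12.5 says the monitoring committee may receive a summary of deaths. It does not require attribution.

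**3. The plan's own figures**

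The exact (Clopper-Pearson) interval for x events in n runs from the 2.5% quantile of Beta(x, n − x + 1) to the 97.5% quantile of Beta(x + 1, n − x).

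- Sensitivity 22/26 = 84.6% (65.1 to 95.6%); the plan gives 85% (65 to 96%).
- Specificity 15/17 = 88.2% (63.6 to 98.5%); the plan gives 88% (64 to 99%).

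All rows of Tables 12 and 13 reproduce to rounding. No stated figure is in dispute; this confirms the inputs and the interval method.

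**4. Exposure under the Section 10.0 assumptions**

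- Enrolled 43, with histology 32: 43 − 32 = 11 without tissue (11/43 = 26%). The plan ascribes these to dropout and inoperable disease, so the number with progression but no tissue lies between 0 and 11.
- Operated without true progression: 32 − 26 = 6, and 6/32 = 18.75%. An observed 6 in 32 would carry an exact 95% interval of 7.2 to 36.4%.
- Assumption: the same share applies to all 11. Then 11 × 0.1875 = 2.1 subjects, with a range of 11 × 0.072 = 0.8 to 11 × 0.364 = 4.0.

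These are subjects without tumour on histology, not subjects with a serious event. The documents give no rate for the latter.

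**5. Effect on a reported rate, n = 43 (illustration)**

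| Events | Rate | Exact 95% CI |
|---|---|---|
| 0 | 0% | 0 to 8.2% |
| 2 | 4.7% | 0.6 to 15.8% |
| 4 | 9.3% | 2.6 to 22.1% |

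For zero events the upper limit is 1 − 0.025^(1/43) = 8.2%. Comparing any row with the first supposes that no other event of that type is recorded.

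**6. Stopping rule**

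Section 5.4.1 needs more than 50% of enrolled subjects with attributed grade 3 or greater toxicity: at least 22 of 43, or 13 of 25 at the review before the 18 added places open (43 − 18 = 25). Two to four omitted events would rarely decide it.

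**The case against.** The strongest reply is that the exemption is narrow. Section 9.4 exempts progression of the cancer, not neurological decline, oedema or pseudoprogression. Its AE definition takes in any unfavourable sign or symptom regardless of cause, and Section 8.1 makes pseudoprogression a separate category. The clinical-progression clause concerns leaving the study and is silent on AE recording. This stands: an event is lost only if it is labelled progression. A reader might infer that the rule itself removes pembrolizumab neurotoxicity, or that the 17 expected pseudoprogressions are all exposed. The text supports neither.

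Second, the investigator is not without information. The limit in Section 4.0 concerns standard imaging at one time point; the protocol adds a repeat scan at four weeks and weekly examinations, and accepts imaging alone to confirm pseudoprogression. This narrows the gap but does not close it, because Section 9 does not require any of that evidence before the exemption applies.

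Third, other records exist. All deaths enter the overall survival analysis, serious events judged drug related are reportable at any time under Section 9.6.4.1, and a separate guidance document on events of clinical interest, not among the documents reviewed, may say more. So the loss is from the safety estimate and expedited reporting, not from the trial.

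Fourth, counting every event without tissue as toxicity would bias the rate the other way: at the assumed share, about 11 − 2 = 9 of 11 would be tumour. This also stands, and it shapes the fix.

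**Conclusion.** The gap is real. The safety sections set no evidentiary standard for progression, Section 8.1 provides ways to be labelled progressed without tissue, and the existing safeguards either rest on the same judgment or act only after an event is already an AE. Serious neurological events or deaths from inflammation can therefore be absent from secondary objective 1 and from expedited reporting.

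The size cannot be determined from the documents. The figure of about 2 subjects (0.8 to 4.0) assumes that all 11 without tissue had progression and share the non-tumour fraction of operated subjects; the true number could be zero. Larger counts of missed serious events, which a reader might reach by adding the 17 pseudoprogressions or treating the histology share as a serious-event rate, have no basis in the plan. Nor do the documents support a claim that the stopping rule is materially weakened. The primary endpoint is untouched, and safety is a descriptive secondary objective in a pilot. This is a cheap improvement worth making, not a defect that invalidates the design.

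**What to change.** Keep the exemption for progression confirmed by tissue as defined in Section 8.1, and say so by cross-reference in Sections 9.4 and 9.6.4.1. In both, add that grade 3 or greater neurological events and deaths ascribed to progression, without tissue showing viable tumour, are recorded, graded and attributed (with possibly related as an option), and reported under a separate category such as *progression not tissue-confirmed*. In Section 10.0, give the AE rate and its exact interval with and without that category. State also how the category relates to the count in Section 5.4.1.

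The cost is a few sentences and more event forms. AE review is already scheduled at suspected and persistent radiographic progression (Section 6.0). Most of the added forms will probably concern tumour, which is why these events should be tabulated separately and not pooled into the toxicity rate.

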9.5 Rescue Medications & Supportive Care

9.5.1 Supportive Care Guidelines

Subjects should receive appropriate supportive care measures as deemed necessary by the treating investigator. Suggested supportive care measures for the management of adverse events with potential immunologic etiology are outlined below and in greater detail in the ECI guidance document. Where appropriate, these guidelines include the use of oral or intravenous treatment with corticosteroids as well as additional anti-inflammatory agents if symptoms do not improve with administration of corticosteroids. Note that several courses of steroid tapering may be necessary as symptoms may worsen when the steroid dose is decreased. For each disorder, attempts should be made to rule out other causes such as metastatic disease or bacterial or viral infection, which might require additional supportive care. The treatment guidelines are intended to be applied when the investigator determines the events to be related to pembrolizumab.

Note: if after the evaluation the event is determined not to be related, the investigator is instructed to follow the ECI reporting guidance but does not need to follow the treatment

guidance (as outlined in the ECI guidance document). Refer to Section 7.12 for dose modification.

It may be necessary to perform conditional procedures such as bronchoscopy, endoscopy, or skin photography as part of evaluation of the event. Suggested conditional procedures, as appropriate, can be found in the ECI guidance document.

9.5.2 Expected AEs due to Pembrolizumab and Guidelines for Management

- **Pneumonitis:**

- For **Grade 2 events**, treat with systemic corticosteroids. When symptoms improve to Grade 1 or less, steroid taper should be started and continued over no less than 4 weeks.
- For **Grade 3-4 events**, immediately treat with intravenous steroids. Administer additional anti-inflammatory measures, as needed.
- Add prophylactic antibiotics for opportunistic infections in the case of prolonged steroid administration.

- **Diarrhea/Colitis:**

Subjects should be carefully monitored for signs and symptoms of enterocolitis (such as diarrhea, abdominal pain, blood or mucus in stool, with or without fever) and of bowel perforation (such as peritoneal signs and ileus).

- All subjects who experience diarrhea/colitis should be advised to drink liberal quantities of clear fluids. If sufficient oral fluid intake is not feasible, fluid and electrolytes should be substituted via IV infusion. For Grade 2 or higher diarrhea, consider GI consultation and endoscopy to confirm or rule out colitis.
- For **Grade 2 diarrhea/colitis** that persists greater than 3 days, administer oral corticosteroids.
- For **Grade 3 or 4 diarrhea/colitis** that persists > 1 week, treat with intravenous steroids followed by high dose oral steroids.
- When symptoms improve to Grade 1 or less, steroid taper should be started and continued over no less than 4 weeks.

- **Type 1 diabetes mellitus (if new onset, including diabetic ketoacidosis [DKA]) or ≥ Grade 3 Hyperglycemia, if associated with ketosis (ketonuria) or metabolic acidosis (DKA)**

- For **T1DM or Grade 3-4 Hyperglycemia**
 - Insulin replacement therapy is recommended for Type I diabetes mellitus and for Grade 3-4 hyperglycemia associated with metabolic acidosis or ketonuria.
 - Evaluate subjects with serum glucose and a metabolic panel, urine ketones, glycosylated hemoglobin, and C-peptide.

- **Hypophysitis:**

- For **Grade 2 events**, treat with corticosteroids. When symptoms improve to Grade 1 or less, steroid taper should be started and continued over no less than

- 4 weeks. Replacement of appropriate hormones may be required as the steroid dose is tapered.
- For **Grade 3-4** events, treat with an initial dose of IV corticosteroids followed by oral corticosteroids. When symptoms improve to Grade 1 or less, steroid taper should be started and continued over no less than 4 weeks. Replacement of appropriate hormones may be required as the steroid dose is tapered.
- **Hyperthyroidism or Hypothyroidism:**
Thyroid disorders can occur at any time during treatment. Monitor subjects for changes in thyroid function (labs every 3 months) and for clinical signs and symptoms of thyroid disorders.
 - **Grade 2** hyperthyroidism events (and **Grade 2-4** hypothyroidism):
 - In hyperthyroidism, non-selective beta-blockers (e.g. propranolol) are suggested as initial therapy.
 - In hypothyroidism, thyroid hormone replacement therapy, with levothyroxine or liothyronine, is indicated per standard of care.
 - **Grade 3-4** hyperthyroidism
 - Treat with an initial dose of IV corticosteroid followed by oral corticosteroids. When symptoms improve to Grade 1 or less, steroid taper should be started and continued over no less than 4 weeks. Replacement of appropriate hormones may be required as the steroid dose is tapered.
 - **Hepatic:**
 - For **Grade 2** events, monitor liver function tests more frequently until returned to baseline values (consider weekly).
 - Treat with IV or oral corticosteroids
 - For **Grade 3-4** events, treat with intravenous corticosteroids for 24 to 48 hours.
 - When symptoms improve to Grade 1 or less, a steroid taper should be started and continued over no less than 4 weeks.
 - **Renal Failure or Nephritis:**
 - For **Grade 2** events, treat with corticosteroids.
 - For **Grade 3-4** events, treat with systemic corticosteroids.
 - When symptoms improve to Grade 1 or less, steroid taper should be started and continued over no less than 4 weeks.
 - **Stevens-Johnson Syndrome (SJS) and Toxic Epidermal Necrolysis (TEN):**
 - One fatal case of SJS in a clinical trial and one fatal case of TEN in the post-marketing setting have been reported in patients treated with pembrolizumab. Including these cases, there have been 8 cases of SJS (6 in clinical trials, and 2 post-marketing) and 2 cases of TEN (both post-marketing) all of which were serious.
 - The risk of SJS and TEN is reported at approximately 0.4 - 7 cases per million patient years in the general adult population.

- Independent risk factors include certain medications such as anticonvulsants, sulfonamides, aminopenicillins, allopurinol, and NSAIDs. Non-medication triggers include infection, contrast media, and vaccinations.
- Malignancy is associated with an increased mortality rate in patients with SJS and TEN.

For signs or symptoms of SJS or TEN, withhold Pembrolizumab and refer the patient for specialized care for assessment and treatment. If SJS or TEN is confirmed, permanently discontinue Pembrolizumab.

- **Immune-mediated myocarditis**

A total of 6 cases of myocarditis have been reported in patients treated with pembrolizumab in clinical trials or in an expanded access program. There were 1 fatal case reported in a clinical trial.

A search of the literature identified neither background incidence rates nor prevalence of myocarditis specifically among cancer patients. Immune-mediated myocarditis should be suspected if other causes of myocarditis, such as infection or prior radiation therapy, have been excluded. Risk factors include certain medications and treatment modalities such as radiation, anthracycline, alkylating agents and most recently checkpoint inhibitors. For suspected immune-mediated myocarditis, ensure adequate evaluation to exclude other etiologies, and administer corticosteroids.

- **Management of Infusion Reactions:** Signs and symptoms usually develop during or shortly after drug infusion and generally resolve completely within 24 hours of completion of infusion.

